#### Patient Calendar:

EOT: End of Treatment; EOS: End of Study

#### CONFIDENTIAL

Release date: Edition number

GED version

## 3.3.3 Retreatment Criteria

Patients may be retreated if all the following criteria are fulfilled:

- Absence of progression or clinical deterioration
- Absence of grade 4 treatment-related non-hematologic AE following the previous administration
- o Resolution of grade 3 or higher adverse event to grade 2 or lower

# 3.3.4 Prevention of Tumor Lysis Syndrome

In order to prevent TLS, several preventative measures should be followed in patients participating in the phase Ib part of the study.

- O Hydration: patients should begin per os hydration 3 days before each of the first 4 infusions of IPH2201 (at least 8 full glasses of water -approximately 2 liters daily). On the day of IPH2201 administration, patients should receive IV fluids (at least 1.5 liter of normal saline) during at least 6 hours, from the first to the fourth administration during the phase Ib. Thereafter, in the absence of TLS, the patient should receive IV fluids (at least 1 liter) during 4 hours on the day of each IPH2201 administration
- Daily administration of allopurinol (200-300 mg/ day) should be given 3 days before and 4 days after the first 4 infusions of IPH220 at week 0 and Week 2 visits (IPH2201 alone) and at Week 4 and Week 6 visits (combined therapy)
- Biology should be frequently monitored from the first to the fourth administration of IPH2201, as
  described in the flow chart foot notes, in synopsis and in section 6 (complete blood count with
  differential and comprehensive metabolic panel 4 hours after the beginning of IPH2201 infusion)

Patients may be initially hospitalized in outpatient facilities. Evidences of TLS should lead in any case to keep the patient hospitalized overnight to infuse at least 4 liters of IV fluids /24hr, or perform an EKG, and, if needed, to begin a continuous cardiac monitoring until the improvement of TLS.

Evidence of TLS may lead the investigator to hospitalize the patient overnight during subsequent administrations, and to monitor closely the biochemistry.

In the absence of clinical and biological sign of TLS during the first 4 IPH2201 infusions, these preventative measures will not be necessary for subsequent IPH2201 infusions.

### 3.4 DURATION OF STUDY

The recruitment of up to 45 patients is expected to approximately cover an 18-month period.

Patients in part 1 may be treated up to 56 weeks: 4 cycles of 2 weeks each followed by 12 cycles of 4 weeks each.

Patients in part 2 may be treated up to 52 weeks: 4 cycles of 2 weeks each followed by 11 cycles of 4 weeks each.

Treatment by ibrutinib will be at least administered until the end of the study follow-up unless a disease progression (IWCLL), untoward toxicity or consent withdrawal leads to the premature interruption of the treatment.

Patients will be followed for 12 months after interruption of IPH2201 treatment (End of Study visit). Furthermore, patients will be enrolled in a post study follow-up enabling the documentation of disease progression (IWCLL) or death for 3 additional years after the completion of their study follow-up.

CONFIDENTIAL

Release date: Edition number

GED version

# 3.5 DISCONTINUATION

### 3.5.1 Discontinuation of the individual treatment

If a patient is progressing at any time during the study, treatment administration will be discontinued and the patient will be withdrawn from the study. For patient withdrawal, see section 5.3.

If a patient discontinues the study for safety reason, disease progression and survival information will be collected.

# 3.5.2 Discontinuation of the study

The sponsor may discontinue the study at any time if an unacceptable toxicity is observed in a patient that leads the safety committee to recommend a transient or permanent discontinuation of the study. If the study is prematurely discontinued, all study data must be returned to Innate Pharma. In addition, the site must conduct final disposition of all unused study drug in accordance with Innate Pharma procedures for the study.

Release date: Edition number

GED version

# 4 STUDY POPULATION

### 4.1 INCLUSION CRITERIA

Patients must meet all of the following criteria for inclusion into the study:

- 1. Confirmed diagnosis of CLL according to the IWCLL classification
- 2. Relapsed, refractory or previously untreated CLL
- 3. CLL requiring treatment according to the IWCLL criteria; patients must be eligible for ibrutinib therapy
- 4. Age ≥ 18 years
- 5. Eastern Cooperative Oncology Group performance status of 0-2
- 6. Life expectancy of ≥ 3 months
- Adequate liver and renal function (total bilirubin ≤ 1.5 X institutional ULN, AST and ALT ≤ 2.5 X institutional ULN, serum creatinine ≤1.5 X institutional ULN or actual creatinine clearance ≥50 mL/min)
- 8. Negative serum pregnancy test within 72 hours before starting study treatment in women with childbearing potential. Women of child-bearing potential and men must agree to use adequate contraception (hormonal or barrier method of birth control; abstinence) prior to study entry and for the duration of study participation, including a minimum of 5 months after last IPH2201 treatment administration
- 9. Ability to understand a written informed consent document
- 10. Signed informed consent prior to any protocol-specific procedures

### 4.2 EXCLUSION CRITERIA

Patients will not be eligible for the study if they fulfil one or more of the following exclusion criteria:

- 1. Patients who have previously received ibrutinib or another inhibitor of BTK
- History of allergic reactions attributed to compounds of similar chemical or biologic composition to ibrutinib
- 3. Central nervous system involvement by CLL
- Abnormal hematological function which is not due to the bone marrow failure related to the CLL (hemoglobin < 9.0 g/dL, absolute neutrophil count <1,000/mm³ and/or platelets <100,000/mm³)

- 5. Patients requiring a treatment by oral vitamin K antagonists
- 6. Serious concurrent uncontrolled medical disorder
- 7. Medical condition or organ system dysfunction which, in the investigator opinion could interfere with absorption or metabolism of ibrutinib
- 8. Moderate or severe hepatic impairment (Child-Pugh classes B and C)
- 9. Active auto-immune disease, which currently or previously required systemic immunosuppressive or immunomodulatory therapy (including corticosteroids administered by systemic route) and/or has a substantial probability to cause an irreversible injury to any tissue and/or is recent or unstable or has a substantial risk to progress and cause severe complication

#### CONFIDENTIAL

Release date: Edition number

GED version

MOD-3783

12 August 2016

10. Abnormal cardiac status with any of the following:

- Unstable angina
- o Myocardial infarction within the last 6 months
- o Arrhythmia requiring treatment and which is not stabilized by the treatment
- QTc > 500ms (Bazett)
- o History of documented congestive heart failure (New York Heart Association functional classification III-IV)
- 11. Pregnant women are excluded from this study; breastfeeding should be discontinued
- 12. Current active infectious disease or positive serology for HIV and/or positive PCR for HCV, or chronic HBV infection (positive Hbs Aq, and in patients treated by IVIG, a positive HBV PCR)
- 13. History of another malignancy within 3 years, except a malignancy, which in the opinion of the investigator is inactive and would not limit survival to less than 5 years
- 14. History of allogeneic stem cell or solid organ transplantation
- 15. Intermittent or continuous renal replacement therapy
- 16. Concomitant treatment with other investigational agents
- 17. Systemic treatment with steroids or other immunosuppressive agents within 30 days prior to entry, but physiological replacement with hydrocortisone or equivalent is acceptable
- 18. Patients who are on chronic treatment with strong or moderate CYP3A4 inhibitors (e.g., nefazodone, aprepitant, ciprofloxacin, diltiazem, erythromycin, fluconazole, grapefruit juice, imatinib, verapamil) or inducers (e.g., carbamazepine, rifampin, phenytoin and St. John's Wort) should be excluded from study entry (see Appendix V)
- 19. Patients should not have psychological, familial, sociological, or geographical conditions that do not permit medical follow-up and compliance with study protocol

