## 3.2 OVERALL DESIGN

This is a multicenter, open label, single arm Phase lb/IIa study, consisting of 2 parts:

- A part 1 dose escalation phase Ib to confirm the safety of IPH2201 as a single agent during 4 weeks and thereafter combined with ibrutinib during 52 weeks
- A part 2 single-arm phase IIa assessment of IPH2201 combined with ibrutinib during 52 weeks
   36 to 45 patients will be enrolled in this clinical study:
  - 12 to 24 patients (3 to 6 patients at each dose level) will be enrolled in the dose-escalation phase lb
  - o Up to 24 patients in the phase IIa

The last 3 to 6 patients treated during the phase Ib with the IPH2201 recommended dose level for the phase IIa (in principle 10 mg/kg) will be included in the efficacy analysis set of the phase IIa part.

If 6 patients (3+3 for safety reasons) are treated during the phase Ib with the IPH2201 recommended dose level for the phase IIa, a maximum of 21 patients will be included in the phase IIa.

If 24 patients were enrolled in the phase Ib of the trial (including 6 at the IPH2201 recommended dose level for the phase IIa), no more than 21 patients would need to be enrolled in the phase IIa. Therefore, the total number of patients will never exceed 45 (24+21).

[figure not shown]

Release date: Edition number

GED version

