### 5.3 CONCOMITANT TREATMENTS

### 5.3.1 Permitted

No pre-medication is to be given at 1st administration to avoid masking the potential risk of infusion reactions. However, from the 2nd administration a pre-medication by acetaminophen or anti-histamine drug might be prescribed, at the investigator discretion, if the patient experienced any grade 1 to 3 infusion-related AE at the previous cycle.

Patients should receive all necessary supportive care in the form of treatment or prophylaxis as clinically indicated e.g. transfusion of blood products, antibiotics, anti-histaminics, analgesics.

Corticosteroids by systemic route are prohibited, as mentioned below in section 5.3.2.

Any blood product and/or concomitant medication administered should be recorded in the medical record and eCRF, including dose, start and stop dates.

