## 5.3.2 Not Permitted

The following concomitant treatments are not permitted until the end of the treatment period (End of Treatment) and must be stopped before the start of treatment accordingly with their pharmacological effects:

- o Any chemotherapy or other systemic anti-tumor therapy (including other monoclonal antibody)
- Any irradiation
- o Corticosteroids IV or *per os* (PO) (except for the treatment of grade ≥ 3 infusion reaction)
- Other Investigational drugs
- o Cytokines and/or growth factors
- Immunosuppressive agents
- o Antivitamin K anticoagulants

Strong CYP3A inhibitors (see appendix V) are contra-indicated if they must be given more than 7 days. If a strong CYP3A inhibitor must be given for 7 days or less consider interrupting ibrutinib until the CYP3A inhibitor is no longer needed.-If a moderate inhibitor (see appendix V) must be given for any time period, the dose of ibrutinib should be reduced to 140 mg. Strong CYP3A inducers (see appendix V) should be avoided with ibrutinib.

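### The protocol accepts patients on physiological hydrocortisone replacement (exclusion 17), but section 5.3.2, read literally, makes them stop it before treatment: the exception was not carried forward

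*Protocol*

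**What the plan says.** **At entry.** Exclusion 17, in Protocol section 4.2 and again in the synopsis, excludes patients with "Systemic treatment with steroids or other immunosuppressive agents within 30 days prior to entry". It then makes an exception: "physiological replacement with hydrocortisone or equivalent is acceptable".

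**On treatment.** Section 5.3.2 sets two conditions on the treatments it lists. Before the first dose, they "must be stopped before the start of treatment accordingly with their pharmacological effects". The bar then lasts through the whole treatment period, since they "are not permitted until the end of the treatment period (End of Treatment"). The list includes corticosteroids given intravenously or by mouth, with one exception in brackets: "except for the treatment of grade ≥ 3 infusion reaction". Immunosuppressive agents are a separate item in the same list.

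**Cross-reference.** Section 5.3.1, on permitted treatments, first allows necessary supportive care in general terms and then says: "Corticosteroids by systemic route are prohibited, as mentioned below in section 5.3.2".

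**Handling of departures.** SAP 5.2 has the sponsor class deviations as major or minor before database lock and commits to summarizing the major ones.

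**The concern.** Hormone replacement is by its nature continuing treatment. A protocol that accepts a patient on replacement should say what happens to it after the first dose. Here the only on-treatment rule that covers it is a ban.

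A site that follows 5.3.2 to the letter has two courses. It can stop a hormone that the patient needs, which is a safety matter. Or it can continue the hormone and give a drug that the protocol prohibits, which produces an avoidable deviation. The second is more likely, because the same protocol has just accepted the patient on that drug. By section 3.4 the treatment period runs up to 56 weeks in part 1 and 52 weeks in part 2, so the question would not pass quickly for any patient concerned.

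**Working it through.** No sample size, error rate or estimate is involved, so there is nothing to recompute. The check sets the texts side by side.

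| Text | Period covered | Rule on systemic steroids | Exception stated |
|---|---|---|---|
| Exclusion 17 (4.2, synopsis) | 30 days before entry | Excludes the patient | Physiological replacement |
| 5.3.2 | Stopped before the first dose, barred until End of Treatment | Intravenous and oral corticosteroids not permitted | Treatment of a grade 3 or higher infusion reaction |
| 5.3.1 | Refers to 5.3.2 | Systemic corticosteroids prohibited | None of its own |

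1. **Is replacement within the 5.3.2 ban?** The corticosteroid item is defined by route, not by dose or purpose, and oral hydrocortisone is an oral corticosteroid. In exclusion 17 the drafters attached an explicit exception for replacement, which suggests that they thought the general wording would otherwise catch it. Section 5.3.2 has no such exception.

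2. **Does the phrase about pharmacological effects lift the ban?** No. It qualifies the instruction to stop before treatment, so it bears on when to stop and not on whether to stop.

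3. **Does the supportive-care sentence in 5.3.1 lift it?** No. The specific prohibition of systemic corticosteroids follows in the same section and governs over the general sentence.

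4. **Can the primary analysis be affected?** The main endpoint population (SAP 4.2.2) is defined by receipt of monalizumab, time since first dose and absence of early progression. It removes nobody for a prohibited medication. The complete response criteria in Protocol 7.1 restrict growth factors, transfusion and erythropoietin but do not mention steroids. The decision rule of at least 4 complete responses in 27 (Protocol 10.2, SAP 3.3.2) is untouched.

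**The case against.** The strongest reply is that 5.3.2 was never aimed at replacement. Exclusion 17 speaks of steroids or other immunosuppressive agents, so the steroids in view are those given to suppress immunity, and replacement is something else. On that reading, with the supportive-care sentence beside it, no site would withdraw needed hydrocortisone, and at most a deviation would be logged. Much of this stands. The intent was probably to allow replacement throughout, and the practical effect is small. What does not stand is that the text already says so: 5.3.2 is worded by route and names a single exception.

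It is also fair to say that the two rules cover different periods. A reader might infer a head-on contradiction within one time window. The documents do not show that. The periods follow one another for the same patient, and the fault is an exception that was not carried from one to the next.

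A reader might also infer that patients on replacement would be withdrawn, since Protocol 4.3 lists major protocol deviations as a ground. Nothing in the documents says that continued replacement would be classed as major, so that step is not supported.

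Finally, a reader might take the planned maximum enrolment as a ceiling on the number affected. Section 4.3.2 replaces patients who stop IPH2201 for progression before 8 weeks. Those patients were treated and therefore subject to 5.3.2, so the enrolment figure does not bound the group.

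**Conclusion.** The inconsistency is real and minor. Followed exactly, 5.3.2 makes an eligible patient stop needed replacement or take a prohibited drug. This is more than a missing detail, because the stated rule itself gives the wrong instruction.

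The number affected is probably small and may be zero. That is a judgement, since the documents give no count of patients on replacement. Exclusion 9 may reduce it further: it removes patients with active autoimmune disease that required systemic immunosuppressive treatment, "including corticosteroids administered by systemic route".

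The consequences are confined to conduct, patient safety and the deviation list. There is no effect on the complete response rate or on the 4-in-27 rule. The conclusion assumes that 5.3.2 is read as written. If sites apply the narrower reading described above, no patient is harmed, and the remaining cost is a possible deviation record that the protocol could have avoided.

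**What to change.** - **Section 5.3.2:** extend the bracketed exception on corticosteroids so that it covers, besides a grade 3 or higher infusion reaction, physiological replacement in the terms already used in exclusion 17.
- **Section 5.3.1:** change the sentence to read that systemic corticosteroids are prohibited with the exceptions listed in section 5.3.2.
- **Exclusion 17:** leave as it is.

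The change needs a protocol amendment with the IRB approval that section 12.2 requires. It alters one list item and one sentence and adds no visit, procedure or patient.

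If treatment has already ended, an amendment serves no purpose. The sponsor should then class any continued physiological replacement as a minor deviation in its list before database lock. Leaving it off the list would not be right: on the written rule it is a deviation, and SAP 5.2 provides only for major or minor. The cost is one line in that list.

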### 4.3 WITHDRAWAL CRITERIA

Patients will be withdrawn from the study in the following situations:

- Disease progression (IWCLL 2008 criteria)
- o Adverse events: a patient may be removed from the study following a severe (grade 3) or life-threatening (grade 4) adverse event at the discretion of the treating physician
- Withdrawal of consent by the patient
- Major protocol deviations (i.e., non-compliance with treatment procedures)
- Investigator's decision
- Sponsor's decision if an inacceptable toxicity observed in another patient led the Safety Committee to recommend a transient or permanent discontinuation of the study

After treatment withdrawal, patients will be followed for at least 4 weeks after last study drug administration or until recovery from all related adverse events to grade 1 or less, or until the toxicity level is stable for at least 6 weeks (except in case of consent withdrawal - see below). The patient will then complete the End of Study (EOS) visit.

After the EOS visit, information on the survival of the patients will be collected periodically by the sponsor through contact with the investigator. In addition, appropriate alternative treatment will be proposed by the investigator to the withdrawn patient.

CONFIDENTIAL

Release date: Edition number

GED version

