### IPH2201 treatment withdrawal:

- o Disease progression (IWCLL 2008 criteria)
- Adverse events: a patient may be removed from the study following a severe (grade 3) or lifethreatening (grade 4) adverse event at the discretion of the treating physician
- o Withdrawal of consent by the patient
- Major protocol deviations (i.e., non-compliance with treatment procedures)
- o Investigator's decision
- Sponsor's decision if an inacceptable toxicity observed in another patient led the Safety Committee to recommend a transient or permanent discontinuation of the study

Release date: Edition number

MOD-3783

12 August 2016

GED version

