# Overall Study Scheme

### 3.3 Administration / Dosage

- o In the part 1 (dose escalation phase Ib) corresponding to the first 12 to 24 patients, IPH2201 is administered as a single agent during the first 2 administrations, at week 0 and week 2; ibrutinib is introduced as a combination therapy from 3rd administration, at week 4.
- o In the part 2 (phase IIa) corresponding to the patients treated at the dose selected by the safety committee, both drugs are administered on the same day from the beginning of the phase IIa, at week 0. On the days scheduled for both IPH2201 and ibrutinib therapy, IPH2201 is administered first, followed by ibrutinib, after end of IPH2201 perfusion.
- o In both parts of the trial, the first 4 administrations of IPH2201 (from week 0 to week 6) occur every 2 weeks. From the 5th administration IPH2201 is administered every 4 weeks.
- Both IPH2201 and ibrutinib may be administered on an outpatient basis
- Treatment by IPH2201 is limited to 56 weeks, or less in the event of a CR with undetectable minimal residual disease documented for 2 months
- Treatment by ibrutinib at least is administered until the end of the follow-up period unless a disease progression (IWCLL), untoward toxicity, or consent withdrawal leads to the premature interruption of the treatment. Patients will be followed 12 months after interruption of IPH2201 treatment

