#### Part 2: phase IIa

In the part 2, phase IIa of the clinical trial, the doses of IPH2201 will be selected by the safety committee.

In case of any grade ≥3 adverse event:

- o Treatment will be temporarily suspended for 2 weeks
- Treatment will be resumed at the same dosage in case of resolution to a grade 2 or lower
- In the absence of resolution to a grade 2 or lower, the treatment suspension will be prolonged by 2 more weeks
- In the absence of resolution to a grade 2 or lower after a 4-week suspension, the patient will be taken off study
- In case of recurrence of a grade 3 related reaction after a temporary suspension, the same suspension will apply, but after resolution to a grade 2 or lower, treatment will be resumed at the lower dose level

In case of IPH2201 treatment discontinuation, the continuation of ibrutinib treatment is left to investigator's discretion.

Release date: Edition number

GED version

12 August 2016 MOD-3783

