# 9.1.2 Adverse Events Collection and Reporting

All AEs and SAEs, whether related or not related to study drug, including those thought to be associated with protocol-specified procedures, must be collected throughout the study from the time of patient signing the consent form until the end of study visit, or until the patient's last study visit. All reported AEs and SAEs will be followed until resolution. The Investigator should take appropriate measures to follow all AEs until clinical recovery is complete and laboratory results have returned to normal, or until progression has been stabilized, or until death, in order to ensure the safety of the patients. This may imply that observations will continue beyond the last planned visit per protocol, and that additional investigations may be requested by the monitoring team up to as noticed by the Sponsor. When treatment is prematurely discontinued, the patient's observations will continue until the end of the study as defined by the protocol for that patient.

All AEs will be recorded on the eCRFs. The records will describe the nature (diagnosis or single syndrome as much as possible, alternatively signs and symptoms) severity, using the NCI CTCAE term (version 4.3 of June 14, 2010), date/time of onset, date/time of end, actions taken with respect to IMP, corrective treatment/therapy given, additional investigations performed, outcome, and causality (relationship to study treatment according to the investigator's assessment).

It will be specified whether the event is serious or not according to the definition of SAE (See section 9.1.1).

A sponsor safety representative will determine the causal relationship when it is not clearly provided by the investigator.

Laboratory, vital signs or ECG abnormalities are to be recorded as AEs only if:

- o Symptomatic and/or
- Requiring either corrective treatment or consultation, and/or
- Leading to IMP discontinuation or modification of dosing, and/or
- Fulfilling a seriousness criterion

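### Protocol sections disagree on whether stopping IPH2201 early ends treatment or ends study participation; under section 4.3 a non-progressing early stopper can have no week-52 response assessment

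*Protocol*

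**What the plan says.** **Stop of treatment.** The synopsis puts progression, adverse events, withdrawn consent, major deviations, investigator decision and sponsor decision under the heading "IPH2201 treatment withdrawal". Protocol 3.3.1 (phase IIa) adds: "In case of IPH2201 treatment discontinuation, the continuation of ibrutinib treatment is left to investigator's discretion". Protocol 3.3 states: "Patients will be followed 12 months after interruption of IPH2201" treatment, and 3.4 says the same. Protocol 9.1.2 has: "When treatment is prematurely discontinued, the patient's observations will continue until the end of the study as defined by the protocol" (the sentence then ends with a reference to that individual patient).

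**Stop of study.** Protocol 4.3 introduces the same six events with "Patients will be withdrawn from the study in the following situations". It asks for a minimum of four weeks' follow-up past the final dose, or until related events recover or stabilise, and then the end-of-study visit. It continues: "After the EOS visit, information on the survival of the patients will be collected periodically". Protocol 3.3.1 also has, for phase IIa: "In the absence of resolution to a grade 2 or lower after a 4-week suspension, the patient will be taken off study". Phase Ib has the same rule after two weeks.

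**Progression after stopping.** Protocol 3.5.1 says: "If a patient discontinues the study for safety reason, disease progression and survival information will be collected". Protocol 4.3.1 places early treatment stoppers in the post-study follow-up, with contact every 3 months for 3 years. Protocol 3.4 describes that follow-up as documenting progression or death. Section 4.3 mentions survival only.

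**Analysis.** SAP 8.1 divides patients with a confirmed CR at week 52 by everyone in the main endpoint population. The only discontinuation that SAP 4.2.2 removes is a stop for progression before 8 weeks. SAP 4.6 imputes nothing.

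**The concern.** A site cannot obey all of these sections for a patient who stops IPH2201 without progressing and stays on ibrutinib. One site could close the patient out, and another could follow the same kind of patient for a year.

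The primary endpoint is affected. It is CR at 52 weeks with marrow confirmation, and the go decision turns on 4 of 27 patients. Each patient is 1/27 = 3.7 percentage points. A patient closed out before week 52 cannot be recorded as a CR at that time but is still counted in the denominator. PFS is also exposed: SAP 8.5 censors at the last disease assessment, which could then be the early end-of-study visit.

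**Working it through.** **1. Which events matter.** For progression, 3.5.1 and 4.3 agree on study withdrawal, and the PFS event has already occurred. Withdrawn consent ends visits under either reading. The conflict therefore bites on adverse events, major deviations, and investigator or sponsor decisions.

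**2. What the two readings give.** Take a phase IIa patient who stops IPH2201 at week 20 for an adverse event, without progression.

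| | Under 4.3 | Under 3.3 and 3.4 |
|---|---|---|
| Visits after stopping | Four weeks at the least, then end of study | 12 months, every 3 months from EOT |
| Earliest close-out | About week 24 | About week 72 |
| Week-52 response | None | Not scheduled as such, but visits fall either side |
| Later progression | 4.3 names survival only; 3.5.1 and 4.3.1 provide for progression | Tumor assessment at each follow-up visit |

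Protocol 7.1 requires the confirming marrow at least 2 months after CR criteria are met, so a close-out at four weeks leaves no room for it.

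Follow-up visits are counted from EOT. With EOT near week 20 and 13-week quarters, they fall near weeks 33, 46, 59 and 72. With EOT near week 13, 26 or 39, one falls near week 52 (13+39, 26+26, 39+13), but only by coincidence.

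**3. Design figure reproduced.** Inputs from SAP 3.3.2: n = 27, positive if at least 4 CR, p0 = 0.05, p1 = 0.20, one-sided alpha 0.05, power 0.80.

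- Power = 1 − P(X ≤ 3 | 27, 0.20) = 1 − (0.0024 + 0.0163 + 0.0530 + 0.1105) = 0.818
- Alpha = 1 − P(X ≤ 3 | 27, 0.05) = 1 − (0.2503 + 0.3558 + 0.2434 + 0.1068) = 0.0437

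The plan's figure holds.

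**4. Effect of unobservable patients.** The documents give no early-stop rate, so the number m is an assumption. If m of 27 cannot have a week-52 CR recorded, X is Binomial(27 − m, p) and the rule stays at 4.

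To see what follow-up could recover, let leavers have true CR probability q and be fully observed: X = Binomial(27 − m, 0.20) + Binomial(m, q). The range q = 0.03 to 0.06 is also an assumption. Protocol 1.1.5.1 reports a 12-month CR rate of 6% on ibrutinib alone in untreated patients. Its 3% for previously treated patients stands in a sentence that speaks of relapses; I read it, from context, as complete response.

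| m | Alpha, leavers unobserved | Power, leavers unobserved | Power, observed, q = 0.03 | Power, observed, q = 0.06 | Recovered |
|---|---|---|---|---|---|
| 0 | 0.0437 | 0.818 | – | – | – |
| 3 | 0.0298 | 0.736 | 0.749 | 0.762 | 1.3 to 2.6 points |
| 4 | 0.0258 | 0.703 | 0.723 | 0.741 | 1.9 to 3.8 points |
| 5 | 0.0222 | 0.668 | 0.694 | 0.719 | 2.6 to 5.1 points |

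If leavers kept the full 20% CR probability, follow-up would restore 0.818, a gain of 8 points (m = 3) to 15 points (m = 5).

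**The case against.** Several stronger readings are tempting, and the documents do not support them.

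- **Progression data are lost.** A reader of 4.3 alone might infer survival-only follow-up. But 3.5.1 collects progression after a safety discontinuation, 4.3.1 read with 3.4 does so through post-study contacts, and 4.3.1 asks for every effort at end-of-study assessments, which include a tumor assessment. What is missing after an early close-out is a scheduled tumor assessment or CT.
- **Section 9.1.2 flatly contradicts 4.3.** Its sentence ends by referring to that individual patient, so it can be squared with an individually early end of study. It is weaker evidence of conflict than 3.3 and 3.4.
- **No early stopper is seen near week 52.** Under 3.3 and 3.4 some are, by coincidence. A patient who stops for CR with undetectable MRD is not on the 4.3 list and keeps the ordinary 12-month follow-up, though it too is counted from EOT.
- **Close-out always comes at four weeks, and late toxicity is missed.** Four weeks is the minimum; recovery or stabilisation may take longer. Removal after an adverse event is discretionary in 4.3. Events are followed to resolution or stabilisation (9.1.2), and possibly related serious events after the end-of-study visit are still notified (9.1.3.1).
- **The whole power loss is recoverable.** After stopping IPH2201 a patient receives at most ibrutinib, so much of the loss may be lost treatment effect that follow-up cannot restore. Counting such patients as non-responders also fits an endpoint defined by what the combination achieves.

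These points narrow the concern. The two incompatible headings over one list remain, as does the missing week-52 response under 4.3. It might be argued that the four-week clock runs from the last ibrutinib dose. But 9.1.1.1 equates study drug with the investigational product, and 5.1 gives that label to IPH2201 only.

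**Conclusion.** The contradiction is real and touches the primary endpoint. The protocol does not settle whether an adverse event, major deviation, or investigator or sponsor decision ends IPH2201 alone or ends participation. It also does not settle whether progression or only survival is recorded afterwards. Under 4.3, a non-progressing early stopper can lack the week-52 response and the marrow confirmation while counting as a non-responder.

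The direction is conservative: the risk is a missed signal at the 4/27 rule, not a false positive. With 3 to 5 unobservable patients, power is 0.74 to 0.67 instead of 0.82. The part that better follow-up would recover is about 1 to 5 points if leavers' CR probability is 3-6%, and more if it is higher. Both the number of leavers and their CR probability are assumptions. The case for change rests on the conflicting text and the low cost of repair more than on the size of the power loss.

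**What to change.** The sponsor should reconcile the synopsis list and Protocol 3.3.1, 4.3 and 4.3.1 with 3.3, 3.4, 3.5.1 and 9.1.2, so that stopping a drug and stopping data collection are separate decisions with separate wording. The text should say once whether progression is collected after each kind of stop.

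For patients who stop IPH2201 without progression, death or withdrawn consent, keep the existing follow-up schedule: tumor assessment, blood counts, adverse events, and CT and marrow when CR or progression is suspected. Add one response assessment at week 52, counted from the start of combined treatment as in SAP 8.1. Which events stop either drug, and what being taken off study means clinically, stays with the sponsor.

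The cost is protocol wording and a few extra visits for early stoppers, including a week-52 assessment that is new for those whose follow-up dates do not fall there.
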